4.0 Study Objectives, Design and Procedures

4.1 Objectives

The objective of this study is to determine the efficacy and safety of multiple doses of ABT-494 versus placebo and to assess the pharmacokinetics of ABT-494 following oral administration in subjects with moderately to severely active Crohn's disease with a history of inadequate response to or intolerance to immunomodulators or anti-TNF therapy.

4.2 Design Diagram

[figure not shown]
This is a Phase 2, multicenter, randomized, double-blind, placebo-controlled study designed to evaluate the efficacy, safety, and pharmacokinetics of ABT-494 as induction

therapy in subjects with moderately to severely active Crohn's disease and evidence of mucosal inflammation defined by a SES-CD ≥ 6 (or ≥ 4 for subjects with disease limited to the ileum) and average daily soft/liquid stool frequency ≥ 2.5 or average daily abdominal pain score of ≥ 2.0 ; and CDAI ≥ 220 and ≤ 450 , with a history of inadequate response or intolerance to immunomodulators and/or anti-TNF therapy. The study will allow enrollment of up to 30% of subjects who were primary non responders to anti-TNF treatment.

The study is designed to enroll approximately 210 subjects to meet scientific and regulatory objectives without enrolling an undue number of subjects in alignment with ethical considerations. Therefore, if the target numbers of subjects have been enrolled, there is a possibility that additional subjects in screening will not be enrolled.

The study duration could be up to 60 weeks, including a Screening Period of up to 35 days, a 16-week double-blind induction period, a 36-week double-blind extension phase, and a 30-day follow-up period. Subjects who met eligibility criteria were randomized in a 1:1:1:1:1:1 ratio to one of the double-blinded induction treatment arms.

[figure not shown]
The schematics of the overall study design are shown in [Figure 1](#) and [Figure 2](#).

Figure 1. Study Design Schematic

*The 6 mg BID dose arm was added to replace the 24 mg QD dose arm in Protocol Amendment 2

**Subjects who were re-randomized at Week 16 to 24 mg QD prior to Protocol Amendment 2 will continue to receive the double-blind 24 mg QD dose until Week 52/PD.

Figure 2. Study Design Schematic for Open-Label Extension Option for Patients Who Do Not Adequately Respond During the Extension Phase

Screening Period

Within 35 days prior to the Baseline Visit, subjects received a full explanation of the study design and study procedures, provided a written informed consent, and underwent the screening procedures as outlined in [Table 1](#).

An e-diary was dispensed and training were provided to the subject at the Screening Visit.

Laboratory tests performed during the Screening period can be repeated in case the abnormalities are considered to be transient by the investigator.

16-Week Induction Period

This period began at the Baseline Visit (Week 0) and end at the Week 16 Visit. At the Baseline Visit, subjects who met all the inclusion criteria and none of the exclusion criteria described in the protocol (Section 5.2.1 and Section 5.2.2) were enrolled into the study and randomized to double-blind induction period. The randomization at Baseline

were stratified by endoscopic disease severity (SES-CD < 15 and \geq 15), prior anti-TNF use (naïve and experienced), and by participation in the substudy of the gene expression in intestinal biopsies (Yes and No). As part of the randomization at Baseline, subjects were randomly assigned (1:1) to have their follow-up ileocolonoscopy done at Week 12 or Week 16. During this period of the study, subjects visited the study site at Weeks 2, 4, 8, 12 and 16. A \pm 3-day window is permitted around scheduled study visits. The last dose of study drug during this period is taken the evening prior to the Week 16 visit.

However, the stratification factor Prior anti-TNF use (naïve and experienced) was added under Amendment 3, and there are less than 10 anti-TNF naïve subjects enrolled under Amendment 3. Therefore, the Prior anti-TNF use will not be included in all analysis as a stratification factor.

Subjects may discontinue study drug treatment at any time during study participation. Subjects that end study participation early will have an Early Termination (ET) Visit and complete the procedures outlined for the ET Visit in [Table 1](#) as soon as possible after the last dose of study drug and preferably prior to the administration of any new therapies.

36-Week Extension Phase

At Week 16, subjects who have completed the induction period will be re-randomized in a ratio of 1:1:1 to one of the three double-blinded doses of ABT-494 3 mg BID, 6 mg BID or 12 mg BID. The re-randomization will be stratified by dose received during the first 16 weeks, and overall response (responder versus non-responder) at Week 16. The subjects who were re-randomized at Week 16 to ABT-494 24 mg QD prior to Protocol Amendment 2 will continue to receive the same double-blind dose until Week 52/PD.

The central reader endoscopic score will be used for calculating the Endoscopic response for the evaluation of the efficacy endpoints. However, for stratification at the time of re-randomization, the endoscopic score at BL from central reader and the endoscopic score at Week 12 or Week 16 from site local reader will be used in order to determine response status.

Clinical response is defined as average daily liquid/soft stool frequency reduction of at least 30% from Baseline and average daily abdominal pain score not worse than Baseline OR average daily abdominal pain score reduction at least 30% from baseline and average daily stool frequency not worse than Baseline.

During this period of the study, subjects will visit the study site at Weeks 20, 28, 36, 44, and 52/Early Termination. A \pm 3-day window is permitted around scheduled study visits. The last dose of study drug is taken the evening prior to the Week 52 visit.

Subjects will be expected to remain on double-blinded therapy throughout the entire 36-week extension phase. However, subjects who are considered by the investigator to have not achieved meaningful symptomatic relief and meet the criteria for inadequate response at or after Week 20 will be eligible to receive the open-label therapy with ABT-494 12 mg BID, [Figure 2](#). Subjects who were re-randomized at Week 16 prior to Protocol Amendment 2 and are taking open-label ABT-494 24 mg QD will be transitioned to ABT-494 12 mg BID.

Subjects who still continue to meet criteria for inadequate response following a 4-week course of open-label ABT-494 12 mg BID will be eligible to dose escalate to open-label ABT-494 24 mg BID.

Subjects with persistent inadequate response while on ABT-494 12 mg BID or 24 mg BID may be withdrawn from the study at the investigator's discretion.

Criteria for Inadequate response are as follows:

- Average daily liquid/soft Stool Frequency > 2.2 OR average daily Abdominal Pain score > 1.8 AND
- An increase level of hs-CRP of at least 1 mg/L from Baseline or a hs-CRP ≥ 5 mg/L, either at the previous visit or at the current visit.

Note: hs-CRP will be performed by Central Lab. However, for the purpose of evaluating Inadequate Response criteria, hs-CRP can also be done at local lab.

Assessment of inadequate response should include consideration by the Investigator to rule out symptoms caused by reasons other than Crohn's disease related inflammation.

In the open-label period, if the subject treated with 24 mg BID has an occurrence of an adverse event thought to be possibly related to study medication that in the opinion of the investigator warrants dose reduction, then the dose can be de-escalated to ABT-494 12 mg BID at the investigator's discretion.

Note: Dose escalation and de-escalation are permitted only once during the study.

Subjects may discontinue study drug treatment at any time during study participation. Subjects that end study participation early will have an ET Visit and complete the procedures outlined for the ET Visit in [Table 1](#) as soon as possible after the last dose of study drug and preferably prior to the administration of any new therapies.

Subjects who are not re-randomized at Week 16 or subjects who early terminated from the study will have a follow-up visit approximately 30 days after the last administration of study drug to obtain information on any new or ongoing adverse events (AEs), and to collect vital signs and clinical laboratory tests.

Follow-Up Period

Subjects who have completed the Week 52 visit will have a follow-up visit approximately 30 days after the last administration of study drug to obtain information on any new or ongoing adverse events (AEs), and to collect vital signs and clinical laboratory tests.

Re-Screen

Subjects that initially screen fail for the study may be permitted to re-screen following re-consent. The subject must meet all the inclusion and none of the exclusion criteria at the time of re-screening in order to qualify for the study. There is no minimum period of time a subject must wait to re-screen for the study. If the subject had a complete initial screening evaluation including the assessment of a purified protein derivative (PPD) test (or equivalent), or Interferon-Gamma Release Assay (IGRA; QuantiFERON-TB Gold test

or T-SPOT TB test), chest x-ray, HBV, HCV and ECG, these tests will not be required to be repeated for re-screening provided the conditions noted in the protocol (Section 5.3.1.1) are met and no more than 90 days have passed.

An endoscopy with biopsy will not be required to be repeated for re-screening provided the conditions noted in the protocol (Section 5.3.1.1) are met and no more than 30 days have passed (from the previous screening endoscopy). All other screening procedures will be repeated. As appropriate, sites are encouraged to contact the AbbVie Medical Monitor to confirm if subjects should or should not be re-screened.

Unscheduled Visits

Unscheduled Visits are for purposes when the subject is coming in for a medical visit for evaluation and assessment. During Unscheduled Visits, blood and urine samples will be obtained for the laboratory tests listed in the protocol (Table 2).

Visits for dispensing new study drug in case of temperature excursion, loss or damage are not considered an Unscheduled Visit. In addition, visits to only retest a lab will not be considered an Unscheduled Visit.

Table 1. Study Activities

| Activity | Screening ^a | Baseline (Week 0) | Wk 2 | Wk 4 | Wk 8 | Wk 12 | Wk 16 | Wk 20 | Wk 28 | Wk 36 | Wk 44 | Wk 52 | Early Termination (ET) Visit | Unscheduled Visit | 30-Day Follow-Up Visit |
|--|------------------------|-------------------|------|------|------|-------|-------|-------|-------|-------|-------|-------|------------------------------|-------------------|------------------------|
| Informed Consent | X | | | | | | | | | | | | | | |
| Inclusion/Exclusion ^b | X | X | | | | | | | | | | | | | |
| Medical/Surgical History ^b | X | X | | | | | | | | | | | | | |
| Prior and Concomitant Medications ^b | X | X | X | X | X | X | X | X | X | X | X | X | X | X | |
| Physical Exam ^c | X | X | X | X | X | X | X | X | X | X | X | X | X | X | |
| Endoscopy ^d | X | | | | | X | X | | | | | X | X | | |
| Biopsy ^e | X | | | | | X | X | | | | | X | X | | |
| SES-CD | | X | | | | X | X | | | | | X | X | | |
| Vital Signs ^f | X | X | X | X | X | X | X | X | X | X | X | X | X | X | X |
| 12-Lead ECG ^g | X | | | | | | | | | | | | | | X |
| Chest X-Ray ^h | X | | | | | | | | | | | | | | X |
| PPD Skin Test or QuantiFERON TB Gold Test ⁱ | X | | | | | | | | | | | | | | |
| Latent TB Risk Factor Questionnaire | X | | | | | | | | | | | | | | |
| Blood Chemistry and Hematology | X | X | X | X | X | X | X | X | X | X | X | X | X | X | X |

Table 1. Study Activities (Continued)

| Activity | Screening ^a | Baseline (Week 0) | Wk 2 | Wk 4 | Wk 8 | Wk 12 | Wk 16 | Wk 20 | Wk 28 | Wk 36 | Wk 44 | Wk 52 | Early Termination (ET) Visit | Unscheduled Visit | 30-Day Follow-Up Visit |
|---|------------------------|----------------------|---------|---------|---------|----------|----------|----------|----------|----------|----------|----------|------------------------------------|----------------------|------------------------------|
| Urinalysis ^j | X | X | X | X | X | X | X | X | X | X | X | X | X | X | X |
| Pregnancy Test ^k | X | X | X | X | X | X | X | X | X | X | X | X | X | | X |
| hsCRP | X | X | X | X | X | X | X | X | X | X | X | X | X | X | X |
| HBV and HCV Screening ^l | X | | | | | | | | | | | | | | |
| ABT-494 Concentration ^m | | | X | X | X | X | X | X | X | X | X | X | X | | |
| Pharmacodynamic biomarkers | | X | | | X | | X | | | | | | X | X | |
| C. difficile toxin | X | | | | | | | | | | | | | | |
| Stool Sample (fecal calprotectin) ^{n,o} | X | | | X | | | X | | X | | | X | X | | |
| Bristol Stool Chart ^p | X | | | X | | | X | | X | | | X | X | | |
| Corticosteroid Taper ^q | | | X | | | | | | | | | | | | |
| Crohn's Disease Activity Index (CDAI) | | X | X | X | X | X | X | X | X | X | X | X | X | X | |
| Inflammatory Bowel Disease Questionnaire (IBDQ) | | X | | | X | | X | | | | | X | X | | |

Table 1. Study Activities (Continued)

| Activity | Screening ^a | Baseline (Week 0) | Wk 2 | Wk 4 | Wk 8 | Wk 12 | Wk 16 | Wk 20 | Wk 28 | Wk 36 | Wk 44 | Wk 52 | Early Termination (ET) Visit | Unscheduled Visit | 30-Day Follow-Up Visit |
|---|------------------------|----------------------|---------|---------|---------|----------|----------|----------|----------|----------|----------|----------|------------------------------------|----------------------|------------------------------|
| European Quality of Life 5 Dimensions (EQ-5D) | | X | | | X | | X | | | | | | X | X | |
| Work Productivity and Impairment Questionnaire (WPAI) | | X | | | X | | X | | | | | | X | X | |
| Abdominal Pain Rating Scale (0 – 10 Scale) | | X | | | | X | X | | | | | | | | |
| Monitor Adverse Events ^r | X | X | X | X | X | X | X | X | X | X | X | X | X | X | X |
| Study Drug Dispensing/Administration | | X | X | X | X | X | X | X | X | X | X | | | | |
| Dispense Subject Diary | X | | | | | | | | | | | | | | |
| Subject Diary Review | | X | X | X | X | X | X | X | X | X | X | X | X | X | |

Table 1. Study Activities (Continued)

| Activity | Screening ^a | Baseline (Week 0) | Wk 2 | Wk 4 | Wk 8 | Wk 12 | Wk 16 | Wk 20 | Wk 28 | Wk 36 | Wk 44 | Wk 52 | Early Termination (ET) Visit | Unscheduled Visit | 30-Day Follow-Up Visit |
|---|------------------------|-------------------|------|------|------|-------|-------|-------|-------|-------|-------|-------|------------------------------|-------------------|------------------------|
| Additional Samples Collection (Optional) | | | | | | | | | | | | | | | |
| Pharmacogenetic ^s | | X | | | | | | | | | | | | | |
| Serologic markers ^t | | X | | | | | X | | | | | | | | |
| mRNA ^t | | X | | | | | X | | | | | | | | |
| Biopsy for gene expression ^u | X | | | | | X | X | | | | | | | | |

Wk = Week

- The Screening period will be a minimum of 7 days but no more than 35 days. Baseline Visit date will serve as the reference for all subsequent visits. A \pm 3-day window is permitted around scheduled study visits.
- Update inclusion/exclusion, prior and concomitant therapy, and medical/surgical history information to assure subject eligibility.
- Physical examination performed at Screening, Baseline, Week 16 and Week 52/Early Termination Visits are full physical examinations which must include an assessment of extra-intestinal manifestations (EIMs) and a count of the number of cutaneous fistulas. Physical examinations and those performed at all other visits are symptom based but must include a count of the number of cutaneous fistulas.
- Colonoscopy at/during the screening period or within 15 days of the Screening Visit will be used to calculate the SES-CD score at Baseline. Subject will be randomly assigned at Baseline to have endoscopy performed at Week 12 or Week 16.
- Biopsy may be done when performing the endoscopy. Biopsy to confirm CD diagnosis may be done when performing the endoscopy if appropriate documentation for confirmation of the diagnosis does not exist. Biopsies to rule out dysplasia and colon cancer may be taken at the investigator's discretion.
- Blood pressure, pulse rate, temperature, respiratory rate and weight should be performed before blood draws are performed. Height will be measured at Screening only (with shoes off and then adding 1 inch or 2.5 cm).
- Subjects with normal ECG within 90 days of Screening would not require a repeat ECG, if documentation is available. Subjects can have a repeat ECG at any time during the study as warranted based on the opinion of the Investigator.

Table 1. Study Activities (Continued)

- h. Chest x-ray includes posterior-anterior (PA) and lateral views. Obtain chest x-ray for subjects with TB risk factors as identified by the TB risk factor questionnaire or for subjects living in areas endemic for TB or for subjects with positive PPD or QuantiFERON-TB Gold. Subjects can have a chest x-ray anytime during the study as warranted based on the opinion of the Investigator.
- i. PPD skin test is to be read 48 to 72 hours after placement.
- j. Dipstick urinalysis will be completed by the sites at all required visits. A microscopic analysis will be performed by the central laboratory, in the event the dipstick results show protein, ketones or blood greater than negative or glucose greater than normal.
- k. Serum pregnancy test will be performed on all women of childbearing potential at Screening and at Week 52/ET. Urine pregnancy test will be performed locally at every visit for all women of childbearing potential. If any urine pregnancy test is positive, a serum pregnancy test will be performed by the central laboratory.
If required by country regulatory authorities, monthly pregnancy tests will be performed throughout the study.
- l. Subjects will be tested for the presence of the hepatitis B Virus (HBV) and hepatitis C Virus (HCV) at Screening. A positive result for the hepatitis B surface antigen (HBs Ag) or hepatitis C (HCV RNA detectable in any subject with anti-HCV Ab) will be exclusionary. For subjects who are negative for HBs Ag but are positive for core antibodies (HBc Ab), HBV DNA PCR will be performed and any result that meets or exceeds detection sensitivity will be exclusionary.
- m. For all subjects, a PK sample will be collected at Week 2, within 1 to 3 hours after dosing, if possible. At Week 4, Week 8, Week 12, Week 16, Week 20, Week 28, Week 36, Week 44 and Week 52/ET, a blood sample for PK will be collected at any time during the visit, and preferably within 1 to 8 hours after the last dose. Patients can take the dose on visit days at their regular schedule and not necessarily at the clinic. The date and accurate time of the PK sample collection and the last ABT-494 dose will be recorded in the CRF to the nearest minute.
- n. Stool sample will be collected at each time point indicated. For the visit that endoscopy will be conducted, stool sample should be collected prior to endoscopy.
- o. A stool sample will be collected for fecal calprotectin analysis at each time point indicated. Subjects will be asked to provide a stool sample at the visit, if possible, or subjects will be sent home with instructions and stool sample supplies (supplies will be provided).
- p. Stool samples for microbiota analysis should be assessed using the Bristol Stool Chart.
- q. Subject is mandated to begin corticosteroid taper at Week 2.
- r. Collection of SAEs begins the day the subject signs the informed consent.
- s. Only if subject provides written consent to collect the pharmacogenetic sample; if the informed consent form is not signed, no pharmacogenetic sample can be collected. The sample is preferred to be collected at BL.

Table 1. Study Activities (Continued)

- t. Only if subject provides written consent to collect the serum biomarkers and mRNA samples; if the informed consent form is not signed, no serum biomarkers and mRNA can be collected.
- u. Only if subject provides written consent to collect biopsy samples for gene expression analysis; if the informed consent form is not signed, no biopsy for gene expression can be collected. Biopsies will be obtained at baseline and as the Week 12/16 endoscopy, based on the colonoscopy assignment for Week 12 or 16.

4.3 Sample Size

Approximately 210 subjects were equally allocated to five treatment groups and the placebo group, representing a randomization ratio of 1:1:1:1:1:1. The sample size for this study was based on the expected proportion of subjects who achieve endoscopic remission at Week 12/16 and on the expected proportion of subjects who achieve clinical remission at Week 16. Assuming an endoscopic remission (as well as clinical remission) rate of 12% in the placebo arm and maximum of 35% in at least one of the ABT-494 BID treatment arms (3 mg BID, 6 mg BID, 12 mg BID and 24 mg BID) at Week 12/16, a sample size of 35 subjects per treatment group is sufficient to test for the presence of a dose response signal, to select the best dose response model for the observed data out of a prespecified set of candidate models, and to estimate target doses of interest (e.g., the minimum effective dose, MED) via modeling using MCP-Mod (Multiple comparison procedure and modeling) approach. This approach provides at least 80% average power to detect a dose effect at 5% level of significance (one-sided) with the linear, E_{max} , exponential, logistic, and sigEmax models pre-specified as likely candidates to characterize the dose-response for ABT-494 for the two co-primary endpoints of clinical and endoscopic remission.

5.0 Analysis Populations

5.1 Definition for Analysis Populations

The intent-to-treat responders (ITT-R) and intent-to-treat non-responders (ITT-NR) analysis sets includes all re-randomized subjects in the double-blind extension phase and are responders and non-responders at Week 16, respectively.

For the ITT-R and ITT-NR analysis sets, subjects are assigned to a treatment group based on the re-randomization schedule, regardless of the treatment actually received. The ITT-R and ITT-NR analysis sets will be used as primary sets for all efficacy analysis. Subjects who were randomized to placebo during the Induction Period will be summarized separately.

The intent-to-treat clinical responders (ITT-CR) and intent-to-treat clinical non-responders (ITT-CNR) analysis sets includes all re-randomized subjects in the double-blind extension phase and are clinical responders and clinical non-responders at Week 16, respectively.

For the ITT-CR and ITT-CNR analysis sets, subjects are assigned to a treatment group based on the re-randomization schedule, regardless of the treatment actually received. The ITT-CR and ITT-CNR analysis sets will be used for sensitivity analysis. Subjects who were randomized to placebo during the Induction Period will be summarized separately.

The safety analysis set consists of all subjects who received at least one dose of study medication in the Extension Phase. For the safety analysis sets, subjects are assigned to a treatment group based on the treatment actually received, regardless the treatment randomized. The safety analysis set will be used for all safety analysis of Extension phase.

Any ABT-494 analysis set will consist of all subjects who received at least one dose of ABT-494 during Induction or Extension. Any ABT-494 analysis set will be used for cumulative safety analysis (from Induction baseline to study end).

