6.0 Analysis Conventions

Definition of Baseline for Induction Period

The Baseline visit date for Induction Period is the date when the first dose of study drug is received and referred to as Day 1 or Week 0. The Baseline value for a variable is defined as the last non-missing value on or before the date of the first dose of study drug for Induction Period.

Definition of Baseline for Extension Phase

The Baseline visit date for Extension Phase is the date when the first dose of study drug for Extension Phase is received and referred to as Day 1 or Week 0 of Extension Phase. The Baseline value for a variable is defined as the last non-missing value on or before the date of the first dose of study drug for Extension Phase.

Definition of Rx Days (Days Relative to the First Dose of Study Drug)

Rx Days are calculated for each time point of interest and it provides a quantitative measure of days between the event and the first dose date. That is, the Rx Day is calculated as the event date minus the date of first dose of study drug plus 1.

The Rx Day will be a negative value when the time point of interest is prior to the date of first dose of study drug, and the Rx Day will be a positive value when the time point of interest is after the first dose date. By this calculation algorithm the first dose day is Rx Day 1, while the day prior to the date of first dose is defined as Rx Day –1 (there is no Rx Day 0). Rx Days are used to map actual study visits to the protocol specified study visits.

Dealing with Multiple Measurements Collected on the Same Day

For efficacy related analyses other than imaging endpoints, if multiple measurements for a particular parameter are collected on the same day for the same subject, the average of those measurements will be used.

For safety related analyses, if multiple measurements are made for a particular laboratory or vital sign parameter on the same day for the same subjects, the average of the values will be used in the analyses of change from Baseline. For summaries and listings for shift from baseline and potentially significant values, all collected values within the pre-specified treatment window will be used.

Definition of Analysis Windows

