11.3 Analysis of Laboratory Data

Changes from Induction Baseline during Extension in continuous laboratory parameters will be summarized by n, mean, standard deviation, and median value value for each treatment group.

Cross (Shift) tables from Induction Baseline to the final value according to the normal range will be provided for each hematology, clinical chemistry parameter and urinalysis parameter except for the microscopic examination.

For selected laboratory parameter with Common Toxicity Criteria (CTC) a listing of all subjects with any laboratory determinations meeting CTC Version 4.03 (or later) of Grade ≥ 3 will be provided. For hemoglobin, an additional list will also be provided based on CTC Version 3.0 (or later) of Grade ≥ 2 . For each of these subjects, the whole course of the parameter will be listed. For subjects with laboratory values with CTC ≥ 3 , all of the laboratory parameters for those subjects will be listed. For subjects with laboratory values with CTC 4, all of the laboratory parameters for those subjects will be listed.

For subjects who switched op open-label therapy, the above tables will also be presented by the open-label dose.

In addition, Cross (Shift) tables from Induction Baseline to the final value according to the normal range will be provided for each hematology, clinical chemistry parameter and urinalysis parameter except for the microscopic examination for the Any ABT-494 analysis set by quartile of average daily dose.

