11.4 Analysis of Vital Signs and Weight

The following vital signs are measured at every visit during the study.

- Body Weight (kg)
- Blood Pressure (Systolic/Diastolic) (mmHg)
- Pulse (bpm)
- Temperature (°C)

Changes from Induction Baseline in vital sign values will be summarized by n, mean, standard deviation, and median value for each treatment group.

In addition, incidence of potential clinically significant results will be summarized.

Criteria for potentially clinically significant vital signs results:

| Vital Sign | Category | Criteria for Potentially Clinically Significant Vital Sign |
|--------------------------|-----------------|---|
| Systolic blood pressure | Low | Value \leq 90 mmHg and decrease \geq 20 mmHg from Baseline |
| | High | Value \geq 160 mmHg and increase \geq 20 mmHg from Baseline |
| Diastolic blood pressure | Low | Value \leq 50 mmHg and decrease \geq 15 mmHg from Baseline |
| | High | Value \geq 105 mmHg and increase \geq 15 mmHg from Baseline |
| Pulse | Low | Value \leq 50 bpm and decrease \geq 15 bpm from Baseline |
| | High | Value \geq 120 bpm and increase \geq 15 bpm from Baseline |

For subjects who switched op open-label therapy, the above tables will also be presented by the open-label dose.

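### The Any ABT-494 laboratory shift tables use Induction Baseline for induction-placebo subjects too, so net change over their 16 placebo weeks enters a table labelled ABT-494

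*SAP*

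**What the plan says.** Membership of the set is defined in section 5.1 of the Extension SAP: "Any ABT-494 analysis set will consist of all subjects who received at least one dose of ABT-494 during Induction or Extension". A subject on placebo in induction who is re-randomised and dosed at Week 16 therefore belongs to it. The following sentence fixes the period: "Any ABT-494 analysis set will be used for cumulative safety analysis (from Induction baseline to study end".

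Section 11.3 applies this to laboratory data. It plans "In addition, Cross (Shift) tables from Induction Baseline to the final value according to the normal range" for haematology, chemistry and urinalysis, "for the Any ABT-494 analysis set by quartile of average daily dose". No other reference value is given for members who started on placebo.

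The by-dose extension tables use the same reference. Section 11.3 has "Changes from Induction Baseline during Extension in continuous laboratory parameters will be summarized" by treatment group, and section 11.4 has "Changes from Induction Baseline in vital sign values will be summarized by n, mean" and other statistics. Section 6.0 does define an Extension Baseline, the "last non-missing value on or before the date of the first dose of study drug for Extension Phase", but sections 11.3 and 11.4 do not use it.

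Two further provisions bear on the point. Section 11.2.1 restricts the system organ class and preferred term table for the Any ABT-494 set to events while on ABT-494. Section 5.1 says that induction-placebo subjects are summarised separately, but attaches this only to the efficacy sets.

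**The concern.** A cumulative any-exposure table should show what happened after exposure began. For subjects who started on ABT-494, Induction Baseline is the last drug-free value and is the right reference. For subjects who started on placebo it is not, because 16 weeks without the drug lie between the reference value and the first dose.

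Those weeks need not be neutral for laboratory values. Protocol section 5.2.3.2 requires corticosteroids to be tapered from Week 2, and active disease can itself move haematology and chemistry in either direction. A lasting change of this kind could be read as a drug effect, or could hide one.

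Extension SAP section 11.1 names laboratory data among the primary safety parameters, and section 11.2.2 lists anaemia, neutropenia, lymphopenia and CPK elevation as events of special interest. The shift tables will be read alongside these. In the by-dose extension tables there is a milder form of the same issue: a change from Induction Baseline can span two regimens but appears under the extension dose alone.

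**Working it through.** The plan states no figure on this point, so there is none to reproduce. The check compares definitions and adds simple arithmetic.

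**Inputs.** About 210 subjects in six equal induction arms (Extension SAP 4.3); 16 weeks of induction and 36 of extension (4.2); re-randomisation 1:1:1 to 3, 6 or 12 mg BID, stratified by induction dose and response (5.2). Retention to Week 16 is not given; 70% to 100% is assumed.

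**1. Which tables are affected.**

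| Planned output for the Any ABT-494 set | Reference or period | Placebo weeks included? |
|---|---|---|
| Laboratory shifts (11.3) | Induction Baseline to final value | Yes |
| AE table by class and term (11.2.1) | Time on ABT-494 | No |
| AE overview (11.2.1) | Unclear whether the same limit applies | Unclear |
| Vital signs (11.4) | No table planned for this set | Not applicable |

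**2. How many subjects.** Induction placebo: 210/6 = 35. Active induction: 210 − 35 = 175, all assumed dosed. With retention r, the placebo share of the set is 35r/(175 + 35r).

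- r = 1.0: 35/210 = 16.7%
- r = 0.9: 31.5/206.5 = 15.3%
- r = 0.8: 28/203 = 13.8%
- r = 0.7: 24.5/199.5 = 12.3%

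**3. What enters the table.** The shift compares two points. For an induction-placebo subject with laboratory values after extension dosing, the first point precedes 16 weeks of placebo and the last follows up to 36 weeks of ABT-494. Only net placebo-period change still present at the last point is carried in. The documents give no rate for such change. If 5%, 10% or 20% of 35 subjects had a lasting category shift from that period (assumed for illustration), the number would be 35 × 0.05 = 1.75, 35 × 0.10 = 3.5 or 35 × 0.20 = 7. The last is 7/210 = 3.3% of the set.

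**4. Effect on the dose quartile.** The time base of average daily dose is not defined. For a placebo subject who completes Week 52, averaging over all 52 weeks multiplies the extension daily dose by 36/52:

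| Extension dose | mg/day from first ABT-494 dose | mg/day over 52 weeks |
|---|---|---|
| 3 mg BID | 6 | 6 × 36/52 = 4.15 |
| 6 mg BID | 12 | 12 × 36/52 = 8.31 |
| 12 mg BID | 24 | 24 × 36/52 = 16.62 |

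A difference of this size can move a subject to another quartile.

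**5. By-dose extension tables.** Three of the six induction regimens are offered under the current re-randomisation. With equal completion across induction arms (assumed), the share keeping the induction regimen is 3/6 × 1/3 = 1/6. For the other 5/6, the change from Induction Baseline spans two regimens. Stratification by induction dose should spread this mix about evenly over the extension arms.

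**6. Under the remedy.** For induction-placebo subjects the maximum shift interval falls from 16 + 36 = 52 weeks to 36, and its placebo part from 16 weeks to 0. Nothing changes for the 175 others, whose last value before ABT-494 is Induction Baseline.

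**The case against.** The strongest defence is that Induction Baseline is the only drug-free value for five of the six induction arms. Extension Baseline for those subjects follows 16 weeks of ABT-494. As the main reference it would remove changes that began in induction and persist, and could show recovery after a lower re-randomised dose as a favourable effect of that dose. This stands, and it is why the by-dose tables should keep their present reference.

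It can also be said that timing is visible elsewhere. The Induction SAP, section 11.3, summarises laboratory changes by induction arm including placebo, and the Extension SAP lists the whole course of a parameter for subjects with Grade 3 or higher values. Grouping by average dose suits subjects whose dose changes. These provisions reduce the harm but do not correct the reference value in the pooled table.

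Four stronger readings are tempting, and the documents do not support them:

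- *That the whole cumulative safety analysis counts placebo time.* The AE table by class and term is already limited to time on ABT-494, and no vital-sign table is planned for this set.
- *That the 16 placebo weeks are themselves reported as ABT-494 shifts.* Only the net change that lasts to the final value is included.
- *That 16/52 = 31% measures the error.* That is a share of follow-up time for a completer; a two-point shift table has no person-time denominator.
- *That the comparison between extension doses is biased.* Re-randomisation was stratified by induction dose, and the extension laboratory and vital-sign tables are descriptive.

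**Conclusion.** The point holds for the Any ABT-494 laboratory shift tables. As written, induction-placebo subjects are given a reference value about 16 weeks before their first ABT-494 dose, although the plan already defines the value they need.

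The number affected is at most 35 of 210. The 12% to 17% share rests on the assumed 70% to 100% retention and on all 175 active-arm subjects having been dosed. How many shift cells would change cannot be derived from the documents.

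For the by-dose extension tables, the use of Induction Baseline is a defensible choice that leaves attribution to the extension dose unclear. It calls for a supplementary table only. No randomised comparison and no efficacy result is affected.

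**What to change.** In the Extension SAP:

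1. **Sections 5.1 and 11.3.** For the Any ABT-494 set, define the laboratory baseline as the last value on or before the first ABT-494 dose. This is Extension Baseline for induction-placebo subjects and Induction Baseline for all others.
2. **Sections 11.2.1 and 11.3.** Define average daily dose, with its time base starting at the first ABT-494 dose.
3. **Section 11.2.1.** State that the AE overview for this set is limited to time on ABT-494, as the table by class and term already is.
4. **Sections 11.3 and 11.4.** In the by-dose extension tables, keep change from Induction Baseline and add change from Extension Baseline as a supplement.

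The cost is a few sentences, one baseline flag and the supplementary tables. No new data are needed: Table 1 already schedules chemistry, haematology, urinalysis and vital signs at Week 16.
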